5.4 Dose Modification Guidelines and Toxicity Management

5.4.1 Purpose and Approach

If a patient experiences a clinically significant and/or unacceptable toxicity with the study treatment, dosing will be interrupted or the dose reduced. Supportive therapy will be administered as required.

If the toxicity resolves or improves to at least Grade 1 or pretreatment baseline (refer to specific toxicity criteria in [Section 5.4.2](#) for danvatirsen and [Section 5.4.3](#) for pembrolizumab) by day 21 for danvatirsen and day 42 for pembrolizumab, dosing may resume.

If the toxicity does not resolve (refer to specific toxicity criteria in [Section 5.4.2](#) for danvatirsen and [Section 5.4.3](#) for pembrolizumab) or at least improve after 21 days for danvatirsen or 42 days for pembrolizumab, dosing may still be resumed after discussion and agreement with the medical monitor.

Dose modification should only be applied if the toxicity is **at least possibly related** to study treatment and in the absence of alternative etiologies.

- When more than one toxicity is noted simultaneously with different grades of severity, the **highest grade** should be used to guide dose modification decisions.
- As one arm of this study is a combination regimen and some side effects of danvatirsen and pembrolizumab can be overlapping (e.g., possible ALT/AST elevations, thrombocytopenia, and neutropenia), every effort should be made to **attribute the toxicity to the component part** of the study treatment regimen, and **only the dose of the component part should be modified**. If the Investigator has any questions with regard to such an AE, the Investigator should immediately contact the Medical Monitor.
- In the absence of clear alternative etiology, all events of an inflammatory nature should be considered immune related.
- The reasons for dose modifications, actions taken, and outcomes will be recorded.
- For concomitant medications, dose modifications will be at the discretion of the Investigator in accordance with the severity of the toxicity.
- For temporary delays in study treatment due to toxicity, the **cycle structure** should **remain** and not be regarded as delayed. Following the resolution of toxicity, the treatment regimen will resume as previously scheduled. This plan will potentially result in skipped doses and is intended to keep the treatment cycles synchronized with study assessments.

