6 DISCONTINUATION AND WITHDRAWAL CRITERIA

6.1 Discontinuation of Study Treatment

After consultation with the medical monitor, patients in the combination arm that are discontinued from one of the study treatments may remain in the study and continue to receive the other study treatment until a discontinuation criterion for the remaining treatment has been met.

Treatment with danvatirsen and pembrolizumab should be permanently discontinued for any of the following:

- Consent withdrawal
- Intolerable AE or an AE that meets the criteria for discontinuation
- Confirmed PD
 - Clinically stable patients who experience radiographic PD by RECIST v1.1 may continue to receive study treatment if patients are otherwise tolerating study treatment in the opinion of the Investigator and there are no signs of rapid, radiographic progression of disease or progression at critical anatomical sites (e.g., cord compression or tumor impinging on a major blood vessel) requiring urgent alternative interventions. Confirmatory imaging should be performed at least 4 weeks later for patients with PD who remain on study treatment. If PD is confirmed, the patient will withdraw from study treatment.
- Clinical progression, in absence of radiographic progression by RECIST v1.1, including intolerable signs or symptoms consistent with disease progression, rapidly worsening laboratory values or relevant tumor markers, rapid decline in ECOG performance status, or impingement of the tumor at critical anatomic sites requiring urgent interventions. Whenever possible, discontinuation due to clinical progression should be discussed with the Medical Monitor
- Pregnancy
- Significant patient non-compliance with the protocol or major protocol deviation
- Investigator decision
- Sponsor decision to end the study.

Patients who discontinue study treatment will complete end-of-treatment (EOT) procedures, safety follow-up, and will enter the survival follow-up phase, as specified in the SoA (Section 8.1). See [Section 7.6](#) for more information.

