## 5.11 Exposure and Compliance to Study Drug

Danvatirsen is an investigational medicinal product (IMP). Pembrolizumab is the standard of care. Collectively, these 2 drugs are referred to as the “study drug”.

The following exposure to study drug parameters will be summarized for the Safety Analysis Set for both Danvatirsen and Pembrolizumab

- Treatment Cycles Completed
- Treatment Duration (Months)
- Treatment Duration of Any Study Drug (Months)
- Number of Doses
- Number of Cycles Infusion Interrupted
- Number of Doses Delayed
- Number of Doses Skipped
- Dose Reductions (Danvatirsen only)

All study drug exposure data will be listed.

QMD Ref: Worldwide-TMP-ST-054-1.0_Effective: 12Aug2022	Governing QMD: Worldwide-SOP-ST-026
Confidentiality Statement	

This document is the property of Worldwide Clinical Trials Inc. and may not be duplicated, copied, altered or removed from company without prior approval from Worldwide Quality Assurance or in compliance with Worldwide Standard Operating Procedures.

Worldwide Clinical Trials Controlled Quality Management Document			
 WORLDWIDE CLINICAL TRIALS	Sponsor:	Flamingo Therapeutics	
	Protocol Number:	FLM-6774-201	
STATISTICAL ANALYSIS PLAN			

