### 5.13.1 Adverse Events

Treatment-emergent adverse events (TEAE) are reported according to protocol as any AE that has an onset on or after the first dose of study drug or any pre-existing condition that has worsened on or after the first dose of study drug up to the subject completion of the study.

A treatment-related AE is defined as an AE as being definitely, possibly, or probably, related to the study drug.

All TEAE summaries will include the number and percentage of subjects experiencing each adverse events as well as the total number of events. The following TEAEs will be summarized separately by system organ class and preferred term, as coded by MedDRA dictionary.

- Any TEAE
- Any TEAE (PT only)
- Related to Any Study Treatment
- Related to Danvatirsen
- Serious
- Serious Related to Any Study Drug
- Leading to Discontinuation of All Study Drugs
- Leading to Discontinuation of Danvatirsen only
- Leading to Discontinuation of Pembrolizumab only
- Leading to Dose Delays or Reductions of Any Study Drug
- Leading to Dose Delays or Reductions of Danvatirsen
- Leading to Death
- Leading to Death Related to Any Study Drug
- Toxicity Grade 3 or Higher
- By Maximum Toxicity Grade

An overall TEAE summary table will be provided separately, tabulating the number of subjects and events for any adverse event for the above categories. The following summaries will also be provided.

- Listing of Serious TEAEs
- Listing AEs Leading of Deaths
- TEAE by Preferred Term
- TEAE Related to Any Study Drug by Preferred Term

QMD Ref: Worldwide-TMP-ST-054-1.0_Effective: 12Aug2022	Governing QMD: Worldwide-SOP-ST-026
Confidentiality Statement	

This document is the property of Worldwide Clinical Trials Inc. and may not be duplicated, copied, altered or removed from company without prior approval from Worldwide Quality Assurance or in compliance with Worldwide Standard Operating Procedures.

Worldwide Clinical Trials Controlled Quality Management Document		
 WORLDWIDE CLINICAL TRIALS	Sponsor:	Flamingo Therapeutics
	Protocol Number:	FLM-6774-201
STATISTICAL ANALYSIS PLAN		

All adverse events will be listed. Listings of AEs leading to death will include a flag for on-treatment deaths. An on-treatment death is defined as death occurring from date of first dose of any study drug to 30 days after last dose of Danvatirsen or 90 days after last dose of Pembrolizumab, whichever is later.

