## STATISTICAL ANALYSIS PLAN

14.2.2.3.7	OS by Region	Stat IP	
14.3.1.1.1	Overall Treatment-Emergent Adverse Events	IP	X
14.3.1.2.1	TEAE by SOC and PT	IP	X
14.3.1.2.1.1	TEAE by PT	IP	X
14.3.1.2.2	TEAE by SOC and PT - Related to Any Study Drug	IP	X
14.3.1.2.3	TEAE by SOC and PT - Related to Danvatirsen	IP	X
14.3.1.2.4	TEAE by SOC and PT - Serious	IP	X
14.3.1.2.5	TEAE by SOC and PT - Serious and Related to Any Study Drug	IP	
14.3.1.3.1	TEAE by PT	IP	
14.3.1.3.2	TEAE by PT - Related to Any Study Drug	IP	
14.3.1.4.1	TEAE by SOC and PT - Leading to Discontinuation of All Study Drugs	IP	
14.3.1.4.2	TEAE by SOC and PT - Leading to Discontinuation of Danvatirsen	IP	
14.3.1.4.3	TEAE by SOC and PT - Leading to Discontinuation of Pembrolizumab	IP	
14.3.1.4.4	TEAE by SOC and PT - Leading to Dose Delays or Reductions of Any Study Drug	IP	
14.3.1.4.5	TEAE by SOC and PT - Leading to Dose Delays or Reductions of Danvatirsen	IP	
14.3.1.4.6	TEAE by SOC and PT - Leading to Dose Delays of Pembrolizumab	IP	
14.3.1.4.7	TEAE by SOC and PT - Leading to Death	IP	
14.3.1.4.8	TEAE by SOC and PT - Leading to Death and Related to Any Study Drug	IP	
14.3.1.5.1	TEAE by SOC and PT - Grade 3 or Higher	IP	
14.3.1.5.2	TEAE by SOC, PT, and Maximum Toxicity Grade	IP	X
14.3.2.1	Listing of Deaths	IP	X
14.3.2.2	Listing of Serious AE	IP	
14.3.4.1	Listing of Lab Abnormalities	IP	
14.3.5.1	Hematology	IP	X
14.3.5.2	Hematology Shift	IP	X
14.3.5.3	Chemistry	IP	
14.3.5.4	Chemistry Shift	IP	X (ALT/AST Only)
14.3.5.5	Coagulation	IP	
14.3.5.6	Coagulation Shift	IP	
14.3.6.1	Extent of Exposure to Danvatirsen	IP	X
14.3.6.2	Extent of Exposure to Pembrolizumab	IP	X
14.3.7.1	Vital Signs	IP	
14.3.7.2	12-Lead ECG	IP	
14.3.7.3	12-Lead ECG Shift	IP	
14.3.7.4	12-Lead ECG Abnormalities	IP	
14.3.7.5	ECOG	IP	
14.3.7.6	Post-Treatment Anticancer Therapy	IP	
Figures			
14.2.3.1.1	Duration of Treatment Swimmer's Plot	IP	X
14.2.3.2.1	Waterfall Plot - Max Percent CFB in Tumor Size	IP	
14.2.3.3.1	Spider Plot - Sum of Target Lesions vs Time by CPS	IP	
14.2.3.4.1	Forest Plot - ORR and DCR	IP	
14.2.3.4.2	Forest Plot - PFS	IP	
14.2.3.4.3	Forest Plot - OS	IP	
14.2.3.5.1	Kaplan-Meier Plot - DOR	IP	
14.2.3.5.2	Kaplan-Meier Plot - DOR by CPS	IP	
14.2.3.5.3	Kaplan-Meier Plot - PFS	IP	X
14.2.3.5.4	Kaplan-Meier Plot - PFS by CPS	IP	X
14.2.3.5.5	Kaplan-Meier Plot - OS	IP	
14.2.3.5.6	Kaplan-Meier Plot - OS by CPS	IP	
14.3.1.1	Spider Plot - AST	IP	X

QMD Ref: Worldwide-TMP-ST-054-1.0\_Effective: 12Aug2022

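### The SAP plans no summary of TEAEs leading to discontinuation of any study drug, and its all-drugs row means two drugs in one arm and one in the other

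*SAP*

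**What the plan says.** SAP 5.13.1 lists the TEAE summaries by system organ class and preferred term. Three concern discontinuation: "Leading to Discontinuation of All Study Drugs", "Leading to Discontinuation of Danvatirsen only" and "Leading to Discontinuation of Pembrolizumab only". The overall TEAE table repeats the same categories. For dose changes the list takes a different basis, "Leading to Dose Delays or Reductions of Any Study Drug", and it also uses an any-drug basis for relatedness and related deaths. It has no any-drug row for discontinuation.

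SAP Section 11 carries three matching tables, 14.3.1.4.1 to 14.3.1.4.3. The last is titled "TEAE by SOC and PT - Leading to Discontinuation of Pembrolizumab", without the word only, and the danvatirsen title drops it too. No any-drug discontinuation table appears there.

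SAP 5.11 defines study drug as danvatirsen and pembrolizumab together: "Collectively, these 2 drugs are referred to as the" study drug. Protocol 6.1 says that combination patients "that are discontinued from one of the study treatments may remain in the study" and continue the other drug, after consultation with the medical monitor. Protocol 5.4.1 asks that toxicity be attributed to a component and that "only the dose of the component part should be modified".

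SAP 5.5 separately summarises, for each drug, how many patients discontinued it and why.

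**The concern.** Safety and tolerability of the combination is the first-listed secondary objective. The protocol also names discontinuations for drug-related toxicity among the signals that the Safety Review Committee looks at. A reader who wants to know whether adding danvatirsen makes more patients stop treatment for toxicity will compare the two columns of the discontinuation rows. The all-drugs row sets a different hurdle in each column: one stop in the control arm, two in the combination arm. The danvatirsen row cannot be populated in the control arm. The pembrolizumab row, as worded in 5.13.1, leaves out combination patients who lost both drugs. On that wording, no AE row answers the question on the same basis in both arms.

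**Working it through.** **Step 1. Classify each kind of stop by the wording of SAP 5.13.1.**

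| What adverse events stop | Arm | All-drugs row | Danvatirsen-only row | Pembrolizumab-only row |
|---|---|---|---|---|
| Pembrolizumab, the only drug given | Control | yes, read literally | no | possible; no rule |
| Pembrolizumab, danvatirsen continues | Combination | no | no | yes |
| Danvatirsen, pembrolizumab continues | Combination | no | yes | no |
| Both drugs, same event | Combination | yes | no | no |
| Each drug, different events | Combination | unclear | possible | possible |

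The first two lines describe the same clinical event, a pembrolizumab stop with nothing else stopped, and they land in different rows. The last line shows why adding the three rows does not reliably give an any-drug total: such a patient can appear twice. A control patient can also appear twice if counted under both the all-drugs and pembrolizumab rows.

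**Step 2. Put the asymmetry into symbols.** The documents give no discontinuation rate, so there is no planned figure to reproduce and every rate below is assumed. Let
- p = probability of stopping pembrolizumab for an AE, the same in both arms;
- q = share of combination pembrolizumab stops in which the same AE also stops danvatirsen;
- e = probability of stopping danvatirsen alone (combination arm).

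The categories are taken as mutually exclusive per patient, and control stops are counted in the all-drugs row.

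| Quantity | Combination | Control |
|---|---|---|
| All-drugs row | p × q | p |
| Pembrolizumab only | p × (1 − q) | not used here |
| Danvatirsen only | e | none |
| Any study drug | p + e | p |

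The expected all-drugs ratio, combination to control, is (p × q)/p = q. It is below 1 whenever q < 1 and does not depend on e, so the row does not register the extra danvatirsen stops.

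**Step 3. One example.** With p = 10%, q = 50%, e = 20%:
- all-drugs row: 0.10 × 0.50 = 5% against 10%;
- any study drug: 0.10 + 0.20 = 30% against 10%;
- pembrolizumab with or without danvatirsen: 10% against 10%.

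**Step 4. A range.** Take p = 5–15%, e = 5–20%, q = 25–100%, with the planned 54 and 27 patients (81 at 2:1). Any-drug discontinuation runs from 5 + 5 = 10% to 15 + 20 = 35% on the combination, against 5–15% on control. The ratio 1 + e/p runs from 1 + 5/15 = 1.3 to 1 + 20/5 = 5. Exact binomial probabilities that the observed all-drugs percentage is strictly lower on the combination are:

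| q | Probability, p = 5% to 15% |
|---|---|
| 25% | 70% to 93% |
| 50% | 60% to 80% |
| 75% | 50% to 63% |
| 100% | 40% to 45% |

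At q = 100% the expected percentages are equal and the result is sampling variation.

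**Step 5. The other reading of the control arm.** If control stops go under pembrolizumab only, that row compares p × (1 − q) with p, which is 5% against 10% in the example. The mismatch moves to another row.

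**Step 6. The Section 11 titles.** Without the word only, the pembrolizumab table compares p with p and is like-for-like. The all-drugs table is still not, and an any-drug figure is still missing.

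**The case against.** Much of the information is planned elsewhere. Disposition counts pembrolizumab stops by reason, by arm, whether or not danvatirsen also stopped, and all adverse events are listed. A reader might infer that the effect of danvatirsen on continuing pembrolizumab cannot be learned from this trial. SAP 5.5 does not support that. What disposition lacks is an any-drug total and a SOC/PT breakdown.

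The Section 11 titles, read as written, may already be the with-or-without tables. Section 11 refers to the TFL shells for final titles, and those are not among the documents. Section 11 also holds a table that 5.13.1 omits (14.3.1.4.6, pembrolizumab delays), so the 5.13.1 list is not the whole specification. This stands, but the text and the titles then define different events and must be reconciled.

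A reader might also infer that the report will show the combination as better tolerated when it is worse. The documents do not establish that. The overall TEAE table shows all categories together, so the danvatirsen stops would be visible beside the all-drugs row. The SAP does not say where control stops go. The overlap q is also unknown. Protocol 5.4.1 points towards single-drug stops. Protocol 5.4.2, on intolerance of the reduced dose, refers to study treatment, the collective term for both drugs in Protocol 5.1.

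Finally, the tables are descriptive, so no test or go/no-go rule depends on them. The tolerability endpoint names interruptions and reductions, for which an any-drug row exists.

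**Conclusion.** The concern holds as a gap in definition and comparability. No any-drug AE-discontinuation summary is planned in SAP 5.13.1 or Section 11. The all-drugs row requires two stops in one arm and one in the other, so it can understate AE discontinuation on the combination. The labels in 5.13.1 and Section 11 differ, and control-arm stops have no counting rule.

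The direction depends on control stops being counted in the all-drugs row and on some combination patients stopping pembrolizumab alone (q < 1). The size is not known: the 5% against 10% and the 1.3- to 5-fold range rest on assumed rates and on equal pembrolizumab stopping in both arms. SAP Section 9 reports early termination, so the final denominators may differ from 54 and 27. That changes the probabilities in Step 4 but not the asymmetry. No error rate is affected. What is missing is a like-for-like safety comparison that data already collected can supply.

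**What to change.** - Add a summary of TEAEs leading to discontinuation of any study drug to SAP 5.13.1, to the overall TEAE table and to Section 11.
- Define the danvatirsen and pembrolizumab rows as discontinuation of that drug with or without the other, which matches the titles of 14.3.1.4.2 and 14.3.1.4.3, and remove the word only from 5.13.1.
- State that a control-arm stop is counted in the any-drug and pembrolizumab rows.
- Keep the all-drugs row as supplementary, since it shows who was left with no study treatment. Add a footnote that it means two drugs in the combination arm and one in the control arm.

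The cost is one additional table and changed selection flags in existing ones. No new data are needed.

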### 5.13.2 Laboratory Data

All laboratory data will be stored in the database with the units in which they are originally reported. Laboratory data in summary tables and subject data listings will be presented in the International System of Units (SI units; Système International d'Unités).

Laboratory parameters will be programmatically graded according to NCI-CTCAE v5.0 toxicity grading, when applicable. For parameters for which a CTCAE scale does not exist, reference ranges from the local laboratory will be used to determine programmatically if a laboratory parameter is below, within or above the normal range for the subject's age and sex. In this case, values low, normal, or high will be assigned.

All laboratory result summaries will be presented separately for chemistry, hematology, coagulation, and urinalysis.

Change from Baseline of numerical laboratory results will be summarized at each visit. A separate summary for categorical urinalysis parameters will be provided.

Shift tables will be provided, showing change in CTCAE toxicity grade from Baseline to last visit as well as Baseline to worst post-Baseline grade. For parameters for which a CTCAE scale does not exist, the shift tables will instead present low, normal, or high, based on provided reference ranges of normal. Only patients with both a Baseline and post-Baseline assessment will be included in the analysis. Scheduled visits, unscheduled visits, and repeat assessments will be considered for worst post-Baseline grade.

In the event that a subject has post-Baseline lab results for the same parameter both above and below the range of normal, the record with the value that is the furthest from the reference range will be considered as the worst. If they are equidistant from the reference range, the worst post-Baseline will be assigned as high.

All hematology, chemistry, coagulation, and urinalysis data will be listed separately. An additional listing will be provided for abnormal laboratory values.

QMD Ref: Worldwide-TMP-ST-054-1.0_Effective: 12Aug2022	Governing QMD: Worldwide-SOP-ST-026
Confidentiality Statement	
This document is the property of Worldwide Clinical Trials Inc. and may not be duplicated, copied, altered or removed from company without prior approval from Worldwide Quality Assurance or in compliance with Worldwide Standard Operating Procedures.	

Worldwide Clinical Trials Controlled Quality Management Document			
 WORLDWIDE CLINICAL TRIALS	Sponsor:	Flamingo Therapeutics	
	Protocol Number:	FLM-6774-201	
STATISTICAL ANALYSIS PLAN			

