5 STUDY TREATMENTS AND CONCOMITANT THERAPY

5.1 Study Treatments

Danvatirsen is the investigational medicinal product (IMP). Pembrolizumab is the standard of care. Collectively, these 2 drugs are referred to as the “study treatments” in this protocol. Information on dose and schedule of administration is provided in [Table 1](#).

Table 1: Doses and Schedule of Administration

Study Treatment Name	Danvatirsen	Pembrolizumab
Unit dose strength	Danvatirsen 50 mg/mL	Pembrolizumab 25 mg/mL
Dosage level	3 mg/kg	200 mg fixed dose
Dose formulation	Concentrate for solution for infusion	Concentrate for solution for infusion
Route of administration	IV infusion	IV infusion
IMP	IMP	Standard of care
Sourcing	Sponsor	Study center
Packaging and labeling	IMP will be provided in glass vials. Each vial will be labeled per FDA requirements.	Commercial package

Abbreviations: FDA = Food and Drug Administration; IMP = investigational medicinal product; IV = intravenous

Danvatirsen will be administered via an IV infusion at 3 mg/kg on Days 1, 3, and 5 of Cycle 1 Week 1 with a ± 1 day dosing window and ensuring there is at least 1 day between each danvatirsen dose, i.e. danvatirsen should not be dosed on consecutive days. Note: The visit windows on D1, D3 and D5 do not apply to patients that are participating in the intense PK subset. Danvatirsen is dosed weekly thereafter beginning on Days 8 and 15 of Cycle 1 and on Days 1, 8, and 15 of each subsequent 3-week cycle. Starting at Cycle 1 Week 2, danvatirsen has a ± 2 -day dosing window.

Pembrolizumab will be administered via an IV infusion on Day 1 of each 3-week treatment cycle after all procedures and assessments have been completed. Pembrolizumab has a ± 7 -day dosing window.

On days when both danvatirsen and pembrolizumab are administered, danvatirsen will be administered first. After a window of at least 60 minutes, pembrolizumab will be administered. In the absence of Grade 2 or greater hypersensitivity reactions, the window of time between the two infusions may be reduced to 30 minutes after the first cycle.

Danvatirsen may be held to allow for recovery of toxicities (See [Section 5.4.2](#) for further guidance on dose modifications). Doses missed during the hold will be considered skipped, and the patient should receive their next dose at the scheduled time.

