7.8 Safety Assessments

7.8.1 Physical Examination

The Investigator or qualified designee will perform a complete physical examination during the screening period, on Day 1 of each cycle, and at the end of the treatment period as specified in the SoA ([Section 8.1](#)). Clinically significant abnormal findings during screening should be captured in the medical history.

Patients on the danvatirsen and pembrolizumab arm will have a targeted physical examination as directed by disease, signs, and symptoms performed on Days 8 and 15 of each cycle and at the 30-day safety follow-up visit. New and clinically significant abnormal findings during the study should be recorded as AEs.

Patients on the pembrolizumab arm will have a targeted physical examination as directed by disease, signs, and symptoms performed on Days 8 and 15 of each cycle through cycle 4 and at the 30-day safety follow-up visit. New and clinically significant abnormal findings during the study should be recorded as AEs. Beginning with cycle 5, patients on the pembrolizumab arm are only required to have an in person visit on Days 8 and 15 if clinically indicated therefore the Investigator or qualified designee will contact the patient via a phone call on Days 8 and 15 to evaluate their general health status and monitor for new AEs and concomitant medications.

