8.1 Schedule of Activities

Table 6: Schedule of Activities

Assessments	Screening	Cycle 1				Cycle 2			Cycle 3 & Cycle 4			Cycle 5 and Subsequent Cycles			Cycle 5 and Subsequent Cycles			EOT ^a (+7D)	Safety Follow-up ^b 30D (+7D)	Safety Follow-up ^b 90D (+7D)	Survival Follow-up Q12W (±7D)
		-28 to 0	D1	D3 ^c & D5 ^c + - 1D	D8 ± 3D	D15 ±3D	D1 ± 3D	D8 ± 3D	D15 ± 3D	D1 ± 3D	D8 ± 3D	D15 ± 3D	D1 ±3D	D8 ±3D	D15 ±3D	D1 ±3D	D8 ±3D ^c	D15 ±3D ^c			
Informed consent ^c	X																				
Demography; baseline characteristics; medical, surgical, and cancer history	X																				
Tumor tissue collection ^d	X					X													X		
Randomization following final confirmation of eligibility ^e		X																			
Complete physical examination ^f	X	X				X			X			X			X			X			
Targeted physical examination ^f			X	X		X	X		X	X		X	X		X	X			X		
ECOG performance status	X	X				X			X			X			X			X	X		
Vital signs ^g	X	X	X	X	X	X	X	X	X	X	X	X	X	X	X	X		X	X		
Height	X																				
Weight ^f	X					X			X			X			X			X	X		
12-Lead ECG in triplicate	X																		X		

Assessments	Screening	Cycle 1				Cycle 2			Cycle 3 & Cycle 4			Cycle 5 and Subsequent Cycles			Cycle 5 and Subsequent Cycles			EOT ^a (+7D)	Safety Follow-up ^b 30D (+7D)	Safety Follow-up ^b 90D (+7D)	Survival Follow-up Q12W (±7D)
		-28 to 0	D1	D3 ^c & D5 ^c + - 1D	D8 ± 3D	D15 ±3D	D1 ± 3D	D8 ± 3D	D15 ± 3D	D1 ± 3D	D8 ± 3D	D15 ± 3D	D1 ±3D	D8 ±3D	D15 ±3D	D1 ±3D	D8 ±3D ^c	D15 ±3D ^c			
Laboratory safety tests (hematology) ^f	X	X		X	X	X	X	X	X	X	X	X	X	X	X	X		X	X		
Laboratory safety tests (serum chemistry) ^f	X	X		X	X	X	X	X	X	X	X	X	X			X		X	X		
Laboratory safety tests (coagulation) ^f	X	X				X			X			X			X			X	X		
Urinalysis ^f	X	X				X			X			X			X			X	X		
Thyroid function tests ^f	X	X				X			X			X			X			X	X		
Pregnancy test ^h	X	X				X			X			X			X			X	X	X	
Concomitant medications ⁱ	X	X		X	X	X	X	X	X	X	X	X	X	X	X ^s	X ^s	X	X			
AE ⁱ	X	X		X	X	X	X	X	X	X	X	X	X	X	X ^s	X ^s	X	X	X	X	
Tumor assessments ^j	X								X			X			X			X			
Danvatirsen ^k		X	X	X	X	X	X	X	X	X	X	X	X	X							
Pembrolizumab ^l		X				X			X			X			X						
Sparse Pharmacokinetics ^m						X						X						X			
Intense Pharmacokinetics ^m		X	X																		
ADA ⁿ		X				X						X						X			
US patients only whole blood, serum, and plasma biomarkers ^o		X		X	X	X			X			X			X			X			

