- o. Whole blood will be collected for the assessment of whole blood, serum, and plasma biomarkers in all US patients at C1D1, D8, and D15; C2D1; C3D1; C5D1; and EOT, as shown in [Table 8](#).
- p. Whole blood will be collected for the assessment of whole blood and plasma biomarkers in all ROW patients at C1D1; C2D1; C5D1; and EOT, as shown in [Table 8](#).
- q. Whole blood will be collected for assessment of PBMC biomarkers in all US patients at C1D1, D8, and D15; C2D1; C3D1; C5D1; and EOT, as shown in [Table 8](#).
- r. C1D3 and C1D5 visits are only applicable to patients on the danvatirsen + pembrolizumab arm. A minimum of one day is required between the D1, D3 and D5 danvatirsen doses. Note: The visit windows on D1, D3 and D5 do not apply to patients that are participating in the intense PK subset.
- s. D8 and D15 AE and concomitant medication assessments for patients on the pembrolizumab arm, may be conducted via a phone call beginning with Cycle 5. In person visits should occur as clinically indicated.

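### From Cycle 5 the combination arm has more scheduled hematology draws than control, so the by-arm worst-grade hematology shift table is biased upward for the combination even with no drug effect

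*SAP*

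**What the plan says.** **Worst-grade rule.** SAP 5.13.2 plans two grade-shift tables per laboratory panel: baseline to last visit, and baseline to worst post-baseline grade. For the second, "Scheduled visits, unscheduled visits, and repeat assessments will be considered for worst post-Baseline grade". SAP 5.2.11 states the same rule for every worst-grade or maximum-grade analysis. SAP 5.4 sets out the columns: each arm and overall. Nothing limits the table to visits common to both arms or adjusts for the number of draws.

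**Visit schedule.** For the period from Cycle 5 on, Protocol 7.8.1 says that "patients on the pembrolizumab arm are only required to have an in person visit on Days 8 and 15 if clinically indicated"; otherwise the site telephones. The last footnote to the Schedule of Activities (Protocol 8.1) adds that "D8 and D15 AE and concomitant medication assessments for patients on the pembrolizumab arm, may be conducted via a phone call beginning with Cycle 5". Protocol 5.1 gives danvatirsen "on Days 1, 8, and 15 of each subsequent 3-week cycle", so combination patients remain in clinic every week.

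**Laboratory marks in the Schedule of Activities.** Hematology is marked on Days 1, 8 and 15 through Cycle 4 for everyone. There are then two blocks headed Cycle 5 and subsequent cycles. The first carries the danvatirsen marks and is therefore the combination's. It has hematology on all three days; the second block has fewer marks. Coagulation is marked on Day 1 only in both blocks.

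**The concern.** A worst-grade summary is a maximum. If one arm is sampled more often, its maximum is higher on average even when the two arms have identical blood counts. Here the arm sampled more often is the experimental one, and the panel concerned is the one most likely to be read for a signal: Protocol 1.1.2 lists thrombocytopenia, anemia and neutropenia among danvatirsen's risks, and safety of the combination is a secondary objective. The Hematology Shift table (14.3.5.2) is marked for the interim report as well as the final one.

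Telephone collection of adverse events does not close the gap. Under Protocol 7.9.5, laboratory abnormalities that need no medical intervention are not recorded as adverse events and are reported with the laboratory data. A silent cytopenia between Day 1 visits would be seen in the combination arm and missed in control.

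**Working it through.** The documents give no draw counts, per-draw abnormality rates or expected worst-grade rates, so there is no stated figure to reproduce. The check counts draws and then asks what the table would show with no drug effect.

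**1. Scheduled post-baseline hematology draws for a patient receiving c cycles.** The draw before the first dose is baseline (SAP 5.2.2). Cycle 1 then gives 2 draws (Days 8 and 15), Cycles 2-4 give 3 each, and the end-of-treatment and 30-day visits give 2.

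- Combination: 2 + 3(c−1) + 2
- Control: 2 + 3(min(c,4)−1) + k·max(0, c−4) + 2

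Here k is the number of control draws per cycle from Cycle 5. I take k = 1 (Day 1 only), because Protocol 7.8.1 makes neither Day 8 nor Day 15 a required visit. Read literally, the misaligned row gives k = 2.

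| Cycles | Combination | Control, k = 1 | Control, k = 2 |
|---|---|---|---|
| 4 | 13 | 13 | 13 |
| 8 | 25 | 17 | 21 |
| 12 | 37 | 21 | 29 |

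On either reading the combination has more draws from Cycle 5, and there is no difference up to Cycle 4.

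**2. Chance that the worst grade reaches a threshold with no drug effect.** Assume a chance p = 2% per draw in both arms (not in the documents). With independent draws the chance over m draws is 1 − (1−p)^m.

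- 4 cycles: 1 − 0.98^13 = 23.1% in both arms.
- 8 cycles: 1 − 0.98^25 = 39.7% v 1 − 0.98^17 = 29.1%. With k = 2, control is 1 − 0.98^21 = 34.6%.
- 12 cycles: 1 − 0.98^37 = 52.6% v 1 − 0.98^21 = 34.6%. With k = 2, control is 1 − 0.98^29 = 44.3%.

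**3. Correlated draws.** Repeated counts in one patient are not independent. With a normal patient effect u and latent intraclass correlation r, the patient's per-draw chance is q(u) = Φ[(Φ⁻¹(p) + √r·u)/√(1−r)], and the rate is the mean of 1 − (1−q(u))^m over u. For k = 1:

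- 8 cycles: 20.0% v 16.4% at r = 0.5, and 10.2% v 8.8% at r = 0.8.
- 12 cycles: 24.1% v 18.3% at r = 0.5, and 11.6% v 9.6% at r = 0.8.

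**4. Average over time on treatment.** Assume exponential time on treatment, the same in both arms, capped at 34 cycles, with p = 2% and k = 1. Gaps are taken before rounding.

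| Median cycles | Share reaching Cycle 5 | r | Combination | Control | Gap (points) |
|---|---|---|---|---|---|
| 4 | 50% | 0 | 29.6% | 23.1% | 6.5 |
| 4 | 50% | 0.5 | 15.7% | 13.6% | 2.1 |
| 4 | 50% | 0.8 | 8.5% | 7.7% | 0.7 |
| 9 | 73% | 0 | 46.4% | 32.5% | 13.9 |
| 9 | 73% | 0.5 | 21.6% | 17.1% | 4.5 |
| 9 | 73% | 0.8 | 10.6% | 9.0% | 1.6 |

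With k = 2 the same formulas give smaller gaps in the same direction: 0.3 to 2.9 points at a median of 4 cycles, and 0.7 to 5.8 at a median of 9.

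**5. Restricting to common draws.** If only draws scheduled in both arms count, the numbers match at every duration (k = 1: 17 v 17 at 8 cycles, 21 v 21 at 12), and the expected difference with no drug effect is zero.

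**The case against.** **It is only descriptive.** No safety test is planned, and the safety objective is to characterize the combination, without the comparative wording of the efficacy objectives. This is correct and limits the harm. But the columns stand side by side, readers will compare them, and nothing in the SAP warns of the unequal sampling.

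**Other planned outputs avoid the problem.** The last-visit shift does not take a maximum, and by-visit summaries use scheduled visits only. Both help, but neither shows a patient's worst value, which is the purpose of a worst-grade table.

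**Clinically indicated visits add control draws.** They enter as unscheduled assessments and narrow the gap for symptomatic abnormalities, but not for silent ones.

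**The laboratory schedule is read from a damaged table.** This also stands. Protocol 7.8.1 and the footnote cover visits, examinations, adverse events and medications, not blood draws. A reader might infer that the combination has three times as many chances per cycle to show an abnormal count. That ratio is the likelier reading, but taken literally the row gives three against two. The text supports more draws in the combination arm, not a firm factor of three.

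**The combination would look more toxic overall.** A reader might infer this too, and the documents do not support it. Coagulation has the same schedule in both arms. Chemistry is reduced from Cycle 5 and is probably Day 1 only in both arms, though its row is misaligned as well. If so, liver enzymes, another named risk, are not affected. Adverse-event tables are largely protected by the Protocol 7.9.5 rule.

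**Conclusion.** The point holds for one output: the worst-grade part of the hematology shift table (14.3.5.2). The direction is certain provided the combination has more hematology draws from Cycle 5, which both readings of the schedule support. Patients who stop by Cycle 4 contribute no bias.

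The size is uncertain. At 2% per draw with Day 1 only in control, it is about 0.7 to 6.5 points for a median of 4 cycles and 1.6 to 14 points for a median of 9, running from strong within-patient correlation (0.8) to independent draws. The per-draw rate, the correlation and the time on treatment are all assumptions. SAP Section 9 reports early termination; if few patients pass Cycle 4, the bias shrinks accordingly.

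A reader might put the excess at 10 to 15 points. That comes from a patient treated through Cycle 10 with independent draws: 17 v 29 draws without the end-of-treatment and 30-day visits, giving 15.7% v 25.3% at 1% per draw and 29.1% v 44.3% at 2%. With correlation of 0.5 to 0.8, the same patient shows a gap of roughly 1 to 5 points. It is an upper illustration, not an expected value.

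**What to change.** 1. Check the hematology and chemistry rows of the Schedule of Activities against the original table, and state in the SAP which draws each arm has from Cycle 5.
2. Keep the all-draws hematology shift-to-worst table as planned, with a footnote that the scheduled draws differ between arms from Cycle 5.
3. Add a supplementary by-arm hematology shift-to-worst table limited to assessments scheduled in both arms: all scheduled draws in Cycles 1-4, Day 1 from Cycle 5, end of treatment and the 30-day visit. If the check shows that chemistry also differs, do the same there.

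The cost is one visit filter, one footnote and one extra table. SAP Section 5 allows this as an amendment before database lock or an addendum after it. The supplementary table will not show Day 8 and Day 15 events after Cycle 4 or findings from unscheduled draws. These remain in the all-draws table, which is why that table should stay and the new one should be additional.
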